- Laboratory tests: CBC with differential, Complete Metabolic Panel (including: sodium, potassium, chloride, CO2, glucose, creatinine, urea nitrogen, calcium, protein, albumin, total bilirubin, ALK Phosphatase, AST, ALT and magnesium),
- ECG

Weekly following the start of the Plerixafor infusion through the end of infusion (+/- 3 days):

- Physical Exam
- KPS
- Vitals
- ECG
- Laboratory tests: CBC with differential, Complete Metabolic Panel (including: sodium, potassium, chloride, CO2, glucose, creatinine, urea nitrogen, calcium, protein, albumin, total bilirubin, ALK Phosphatase, AST, ALT and magnesium)
- Phase I only: PKs
- Change infusion bag of Plerixafor
- Review concomitant medications and adverse events
- On the last day of infusion, an SDF level will be checked (+/-1 week)
- Biweekly following the start of Plerixafor infusion through the end of infusion (+/- 3 days):Laboratory tests: Troponin

4 weeks after the end of XRT (+/- 7 days):

- MRI brain with and without contrast
- Start monthly TMZ

Concomitant medications and adverse events will be followed up until 30 days after the end of the Plerixafor infusion.

Investigator will manage monthly TMZ per their standard practice. Follow up MRIs will be done per standard of care (approximately every 8-12 weeks).

6 months after the start of XRT (+/- 2 weeks):

• MRI brain with and without contrast

Post-Progression Follow-Up:

Unless a patient has specifically withdrawn consent to be followed for survival, he or she will be

Version #11, Date: 04-29-2015 Page 24 of 52

contacted (by phone or clinic visit) every 12 weeks (+/- 2 weeks) following disease progression to collect data regarding survival status and subsequent anticancer therapy. Follow up will continue for either 5 years or until death, withdrawal, lost to follow up, or study termination.

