4.1 General Concomitant Medication and Supportive Care Guidelines

The use of all standard supportive medication, including appropriate antimicrobrial prophylaxis for chemotherapy, is permitted, although concurrent treatment with immunosuppressive or immunomodulatory agents is discouraged. Concomitant systemic corticosteroids are to be avoided if at all possible. If used, doses of steroids should be the minimum necessary for appropriate clinical management.

The following are prohibited while on study:

- Other investigational agents
- Any concurrent chemotherapy, radiotherapy, hormonal therapy, immunotherapy, or other systemic therapy for cancer

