4.3 Alternatives

The study participant would be eligible for standard of care treatment protocols or any additional investigational trials (per eligibility requirements) should withdrawal from our study be warranted.

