10.2.2 Measurement Definition

This endpoint of PFS6 months post start of chemoradiation will be assessed using RANO criteria.

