10.2.4 Measurement Time Points

An MRI will be done 35+/-3 days after the completion of XRT. Follow up MRIs will be done per standard of care (approximately every 8-12 weeks), with one occurring 6 months post the start of radiation, until progression or withdrawal of consent.

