12.4 Primary Analysis

For the Phase II component, it is expected that no more than 50% of patients will have stable disease at 6 months (defined as stable MRI and clinical status, including being on a stable dose of steroids and not on bevacizumab). We will therefore consider this regimen of interest if significantly more than 50% of patients achieve this benchmark.

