12.5.2 Analysis Plan

For the Phase II component, it is expected that no more than 50% of patients will have stable disease at 6 months (defined as stable MRI and clinical status, including being on a stable dose of steroids and not on bevacizumab). We will therefore consider this regimen of interest if significantly more than 50% of patients achieve this benchmark.

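### The 6-month success definition excludes only bevacizumab, so a scan-stable patient who starts other antitumour therapy before progression meets the benchmark, and a switch in about the second half of the window has no planned record

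*Combined protocol and SAP*

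**What the plan says.** **Success definition.** Sections 12.4, 12.5.2 and 12.7 give the same benchmark for 6-month stable disease: "defined as stable MRI and clinical status, including being on a stable dose of steroids and not on bevacizumab". Bevacizumab is the only anticancer treatment named.

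**Endpoint.** Section 10.2.2 states: "This endpoint of PFS6 months post start of chemoradiation will be assessed using RANO criteria". The progression criteria in 10.2.3 cover enhancing and non-enhancing disease, new lesions and clinical deterioration. Starting a new therapy is not among them. Section 12.2 plans Kaplan-Meier estimates of PFS without a censoring rule.

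**Leaving treatment or study.** Section 4.2 lists reasons other than progression, including DLT, unacceptable toxicity and investigator decision. Section 4.3 then opens standard care or "any additional investigational trials (per eligibility requirements) should withdrawal from our study be warranted". MRI follow-up under 10.2.4 runs "until progression or withdrawal of consent".

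**Prohibition.** Section 4.1 introduces its list with "The following are prohibited while on study" and names other investigational agents and other cancer therapy. It says nothing about scoring.

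**Recording.** Section 4.0.1 has two provisions: "Concomitant medications and adverse events will be followed up until 30 days after the end of the Plerixafor infusion", and contact every 12 weeks "following disease progression to collect data regarding survival status and subsequent anticancer therapy".

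**The concern.** The plan already accepts that a later treatment can produce a stable 6-month scan that should not be credited to the regimen; that is the evident purpose of excluding patients on bevacizumab. It does not apply this principle to any other agent, to further radiotherapy or to another trial's drug. The study is open-label, and the investigators judge progression (4.2, 10.2.5), so treatment can be changed on an equivocal scan without progression being declared.

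At stake is what the single-arm comparison with 50% means. A success counted after a switch reflects the regimen plus whatever followed, and there is no concurrent control in which the same thing would happen. If the switch is also not captured on a form, the report cannot show from planned data how many successes are of this kind. The plan's own criterion is affected too: beyond the concomitant-medication window, no scheduled collection records bevacizumab in a progression-free patient.

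**Working it through.** **1. Does the written rule score a switcher as a success?** Take a patient who starts a non-bevacizumab antitumour therapy before progression and has a stable scan, clinical status and steroid dose at 6 months.

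| Section | Effect on scoring |
|---|---|
| 12.4, 12.5.2, 12.7 | All listed conditions met; not on bevacizumab: success |
| 10.2.2, 10.2.3 | No progression criterion met: progression-free |
| 4.1 | A protocol deviation if still on study; no scoring consequence |
| 10.2.4 | Scans continue to progression or withdrawal of consent; a new therapy does not end them |
| 12.2 | No censoring rule |

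Applied as written, the patient is a success.

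**2. How much of the window lacks planned recording?** Inputs: irradiation over six weeks (2.4), so 42 days; infusion starts 7 days before it ends (2.4); infusion of 2 or 4 weeks (5.1); medications followed for 30 days after infusion (4.0.1); assessment 6 months from the start of radiotherapy (1.1, 4.0.1, 10.2.2), taken as 183 days.

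- Infusion start: 42 − 7 = day 35.
- 4-week infusion: ends at 35 + 28 = day 63; recording ends at 63 + 30 = day 93; gap 183 − 93 = 90 days, and 90/183 = 49%.
- 2-week infusion: ends at 35 + 14 = day 49; recording ends at 49 + 30 = day 79; gap 183 − 79 = 104 days, and 104/183 = 57%.
- With the ±2-week window on the 6-month MRI, the gaps are 76 to 104 days and 90 to 118 days.

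**3. What can one patient do to the decision?** Phase II has n = 20 (12.5.1) and the benchmark is 50% (12.5.2). The plan requires significantly more than 50% but gives no test, alpha or sidedness, so it has no cut-off to reproduce. Assumption: exact binomial test, one-sided alpha 0.05.

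P(X ≥ r) = Σ C(20,k) / 2^20, summed over k = r to 20, with 2^20 = 1,048,576.

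- r = 15: 21,700 / 1,048,576 = 0.0207
- r = 14: 60,460 / 1,048,576 = 0.0577

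The cut-off is 15/20, and also at one-sided 0.025. Rescoring one patient turns 15/20 into 14/20 and significance into non-significance. At one-sided 0.10 the cut-off is 14/20, and 13/20 gives 0.1316, so one patient again decides.

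Each patient is 1/20 = 5 points. This is a ceiling: it applies in full only if the patient would otherwise have failed.

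**4. False-positive rate under an assumed amount of switching.** Suppose the true success rate without switching is 50%, and a share s of failures is scored as success because of other therapy. Then p = 0.5 + 0.5s. The documents give no value for s; the range is an assumption.

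| s | p | P(X ≥ 15 of 20) |
|---|---|---|
| 0 | 0.500 | 0.021 |
| 5% | 0.525 | 0.035 |
| 10% | 0.550 | 0.055 |
| 20% | 0.600 | 0.126 |
| 30% | 0.650 | 0.245 |

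**5. The looser synopsis wording.** The synopsis calls anything above 50% a positive signal. Under that rule two such patients would move 9/20 (45%) to 11/20 (55%) and across the line. They would not under 12.4, 12.5.2 or 12.7: P(X ≥ 11) = 0.41.

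**The case against.** The strongest reply is that the gap is narrower than it looks, and most of that reply stands.

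- *Recording.* A reader might infer that other therapy is recorded only after progression. It is not: medications are followed to about day 79 or 93. Nor does it follow that a switch could never be examined later. Section 10.1.4 plans monthly clinic visits after treatment, the benchmark itself requires someone to establish bevacizumab status at 6 months, and an on-study switch breaches 4.1 and would come to the DSMC as a deviation (11.2). What is missing is planned, dated collection in a progression-free patient during the later part of the window.
- *Direction.* A reader might infer that bias can run only towards a positive result. The documents do not settle this. A patient removed under 4.2 may have no 6-month scan, despite 10.2.4, and could be treated as missing, non-evaluable or failed. Some handling of removals would lower the rate.
- *Other safeguards.* Unstable MRI, clinical status or steroid dose already voids a success, and clear tumour-related deterioration is progression under 10.2.3. Only patients stable on every listed element are at issue.
- *Size.* Nothing in the documents says how many patients would switch, and some switchers would have succeeded anyway.

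None of this supplies the missing scoring rule. A ban on a treatment does not say how to score a patient who receives it, and the ban in 4.1 lapses once the patient is off study.

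**Conclusion.** The point holds and should be fixed, though it does not undermine the design. The benchmark as written counts as a success any patient stable on scan, clinical status and steroids who has started non-bevacizumab antitumour therapy before documented progression. Such a switch has no planned record for about 90 of 183 days after a 4-week infusion, or about 104 after a 2-week one.

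The effect on the result cannot be estimated from the documents because the number of switchers is unknown. It is at most 5 points per patient, and one patient can decide the outcome at the cut-off (p = 0.021 against 0.058). That rests on an assumed exact test at one-sided 0.05. The false-positive figures also rest on the assumed share of failures rescored. The 45%-to-55% example bears only on the synopsis rule.

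**What to change.** 1. In 10.2.2, 12.4, 12.5.2 and 12.7, widen the bevacizumab condition to: *no antitumour therapy other than protocol radiotherapy, temozolomide and Plerixafor started before documented progression*. A patient who starts such therapy has not achieved PFS6.
2. Apply the same scoring rule to patients removed from study without progression, and say how a removed patient with no 6-month MRI is classified.
3. In 4.0.1, record the type and start date of any such therapy through the 6-month MRI, whatever the progression status.
4. Report the number of patients affected, with a sensitivity analysis that scores them on RANO status alone.

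Tumour found at re-operation should not by itself be written in as failure. Biopsy-only and partially resected patients are eligible (3.1.3), so residual tumour need not mean progression.

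The cost is a few lines of text and a short CRF entry for therapy type and start date. Scoring and data collection change; what patients may receive does not. The downside is a slightly lower PFS6 when a patient switches for reasons unrelated to the tumour, which the sensitivity analysis will show.

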4.1 General Concomitant Medication and Supportive Care Guidelines

The use of all standard supportive medication, including appropriate antimicrobrial prophylaxis for chemotherapy, is permitted, although concurrent treatment with immunosuppressive or immunomodulatory agents is discouraged. Concomitant systemic corticosteroids are to be avoided if at all possible. If used, doses of steroids should be the minimum necessary for appropriate clinical management.

The following are prohibited while on study:

- Other investigational agents
- Any concurrent chemotherapy, radiotherapy, hormonal therapy, immunotherapy, or other systemic therapy for cancer

4.2 Criteria for Removal from Study

The investigator has the right to discontinue a patient from study drug or withdraw a patient from the study at any time. In addition, patients have the right to voluntarily discontinue study drug or withdraw from the study at any time, for any reason. Reasons for discontinuation or withdrawal include, but are not limited to:

- Patient withdrawal of consent
- Progression of disease by RANO criteria, as determined by the investigator
- DLT (any AEs with suspected causal relationship with Plerixafor >= grade 3 including ECG changes indicative of ischemia, ventricular tachycardia)
- Investigator decision (eg, symptomatic/clinical deterioration or not in the patient's best interest to continue in the study)
- Patient is lost to follow up
- Death
- Non-compliance of the patient with protocol mandated procedures
- Any unacceptable toxicity

4.3 Alternatives

The study participant would be eligible for standard of care treatment protocols or any additional investigational trials (per eligibility requirements) should withdrawal from our study be warranted.

5. INVESTIGATIONAL AGENT/DEVICE/PROCEDURE INFORMATION

5.1 Investigational Agent/Device/Procedure

The drug Plerixafor (AMD3100) will be supplied in infusion ready vials containing 10 ml of 20 mg/ml solution (which is stable for several months at room temperature) by Sanofi. There are no known incompatibilities of the agent with commonly used intravenous solutions. There is no need to administer the agent with food and there are no pre-medications necessary. There are no

Version #11, Date: 04-29-2015 Page 25 of 52

restrictions against any medications and pre-medications may be used on an as needed basis.

The four possible dose levels are:

- 200 μg/kg per day for 2 weeks
- 200 μg/kg per day for 4 weeks
- 400 µg/kg per day for 4 weeks
- 100 μg/kg per day for 4 weeks

The starting dose in the Phase I is 200 µg/kg per day for 4 weeks

Dose will be based on weight at screening and will not be modified. Actual body weight will be used to calculate dose except in patients who are overweight. The dose of Plerixafor will be adjusted for patients who weigh > 30% over their Ideal body weight. IBW is calculated as follows:

```
Males: IBW (kg) = 50.0 + [(2.3)(Height in inches – 60 inches)]
= 50.0 + [(2.3)(Height in cm)(0.39370079) - 60)]

Females: IBW (kg) = 45.5 + [(2.3)(Height in inches – 60 inches)]
= 45.5 + [(2.3)(Height in cm)(0.39370079) – 60)]
```

```
The ABW is calculated as follows:

ABW (kg) = IBW + 0.4(actual weight - IBW)
```

Plerixafor will be prepared weekly by the investigational pharmacy, with each dose being prepared no more than 4 hours prior to its use. Per Stanford Investigational Pharmacy policy, the pharmacy will prepare sterile products in an environment that complies with USP 797 parameters. The IV admixture area is kept clean and orderly and a demarcation line identifies the separation of the anteroom from the buffer area. Corrugated boxes are not allowed in the anteroom. A clean cart/dirty cart system is used to transfer inventory and compounding supplies into and out of the cleanroom

Infusion bags will be changed every week while the patient is coming for follow up. Plerixafor will be infused using a 0.2 micron in-line filter that will be changed with each new dose for all administrations. The volume prepared by the investigational pharmacy will be determined to allow a fixed infusion rate of 1.5 mL/hour.

As per previously published technique, Plerixafor will be suspended in normal saline to the final solution [30]. The minimum rate will need to be 0.5 mL/hour to keep the picc line patent however the rate of infusion will be modified accordingly per the volume used in the dilutent

Please see "Investigator's Brochure" and section 2.5 above

Page 26 of 52

5.2 Availability

Plerixafor is supplied in open-label 2 mL glass vials containing 1.7 mL of a 20 mg/mL sterile solution. Each Plerixafor vial will be used to provide a single dose only. Remaining drug solution in each vial must not be used. Each vial will be affixed with a label describing the protocol number, content of each vial, lot number, required cautionary statements or regulations, storage conditions, and the Sponsor's name and address.

The investigational product is shipped in cartons containing five (5) Plerixafor vials each. Each carton will also be affixed with a label describing the protocol number, contents of each carton, lot number, required cautionary statements or regulations, storage conditions, and the Sponsor's name and address.

The investigational product will be stored at room temperature (15-30°C) in a secure location accessible only by authorized personnel. All drug supplies are to be used only for this protocol and not for any other purpose.

5.3 Agent Ordering

Plerixafor will be ordered using the Investigator Sponsored Trial (IST) portal at http://www.saists.com.

5.4 Agent Accountability

All Plerixafor sent to the site will be accounted for. In addition, the volume of Plerixafor dispensed for each patient will be recorded on an Investigational Product Accountability Log and the volume administered documented on the case report form (CRF). An accurate record of the date and amount of Plerixafor dispensed to each patient will be available for inspection at any time. Partially used vials may be destroyed per institutional guidelines and documented. All unopened and unused vials of Plerixafor will be destroyed upon completion of the study protocol or if drug expires unless otherwise directed by the Sponsor. The study site will document all receipt, complete destruction, and return (if applicable) of Plerixafor.

6. DOSE MODIFICATIONS

There will be no dose modifications or delays for an individual patient's dose except in the circumstance of moderate to severe renal impairment. If a patient has a Creatinine clearance less than or equal to 50 mL/min, the dose of Plerixafor will be reduced by one-third.

6.1 Dose Limiting Toxicities

DLT is defined as any hematologic or non-hematologic AE grade ≥3 with a suspected causal relationship to Plerixafor (including including ECG changes indicative of ischemia, ventricular tachycardia).

- Patients will be monitored for DLTs for 5 weeks from the start of the Plerixafor infusion.
- DLT's in the first cohort may occur before or after 14 days. If a DLT occurs in weeks 3 or 4 of treatment, we will treat next patient with a dose of 200 μg/kg/d x2 weeks. If a DLT occurs from the start of treatment through the second week of treatment, we will

Version #11, Date: 04-29-2015 Page 27 of 52

treat next patients at a dose of 100 μ g/kg/d x 4 weeks. If a patient experiences a DLT, the infusion will be discontinued. The next patient treated at the lower dose level as dictated by the mTPI table. If an early dose limiting toxicity occurs at lowest dose level (200 μ g/kg/d x 2 wk or 100 μ g/kg x 4wks) then the protocol will be stopped at that point.

6.2 Infusion Reactions

For the start of the Plerixafor infusion, all patients will be closely monitored on site for at least 6 hours. All patients will be evaluated weekly by a physician for the duration of the infusion.

All patients will be provided the contact information for the 24 hour on call pharmacist and neurology physician.

For Grade 1 and 2 allergic reactions to Plerixafor infusion: oral steroids or antihistamine. Patients may be discontinued at investigator's discretion

For Grade 3 and higher allergic reactions: Standard allergy treatment could include intravenous solumedrol, intravenous Benadryl, and possibly epinephrine at the discretion of the treating physician. Plerixafor infusion will be discontinued.

7. ADVERSE EVENTS AND REPORTING PROCEDURES

7.1 Potential Adverse Events

Safety will be assessed by monitoring clinical and laboratory evaluations and AEs.

Definitions

Adverse Event

An AE is any untoward medical occurrence associated with the use of the investigational product (active or placebo drug, biologic, or device) in a clinical investigation patient, which does not necessarily have a causal relationship with the investigational product. An AE can, therefore, be any unfavorable and unintended symptom, sign, disease or condition, or test abnormality whether or not considered related to the investigational product.

AEs may include, but are not limited to:

Subjective or objective symptoms spontaneously offered by the patient and/or observed by the investigator or medical staff

Clinically significant laboratory abnormalities

A significant worsening of the patient's condition from study entry

Disease signs and symptoms and/or laboratory abnormalities existing prior to the use of the study treatment that resolve but then recur after treatment

Disease signs and symptoms and/or laboratory abnormalities existing prior to the use of the study treatment which increase in frequency, intensity, or a change in quality after treatment

Version #11, Date: 04-29-2015 Page 28 of 52

Since prior studies using this medication have included premature ventricular contractions (PVCs), there will be a temporary interruption of plerixafor treatment for abnormalities in serum magnesium, calcium, or potassium at a Grade 2 or more severe. The study medication may be resumed following correction of these electrolyte abnormalities as confirmed by repeat serum level testing. Supplementation to include magnesium sulfate, calcium carbonate, or potassium chloride may be used as clinically indicated.

Serious Adverse Events (SAEs)

A SAE is any adverse event that results in any of the following outcomes:

- Death
- A life-threatening experience
- Requires inpatient hospitalization or prolongs existing hospitalization
- A persistent or significant disability/incapacity
- A congenital anomaly/birth defect
- Important medical events that may jeopardize the patient and may require medical or surgical intervention to prevent 1 of the outcomes listed above

Hospitalizations that occur under the following circumstances are not considered to be SAEs:

- were planned before entry into the clinical study;
- are for elective treatment of a condition unrelated to the studied indication or its treatment;
- occur on an emergency or outpatient basis and do not result in admission (unless fulfilling the criteria above), are part of the normal treatment or monitoring of the studied indication and not associated with any deterioration in condition.

Severity

The investigator will grade AEs using the National Cancer Institute (NCI) Common Terminology Criteria for Adverse Events (CTCAE) (version 4.03, May 2009). Grades refer to the severity of the AE. The CTCAE v 4.03 displays Grades 1 through 5 with unique clinical descriptions of severity for each AE based on this general guideline:

Grade	Description
1	Mild; asymptomatic or mild symptoms; clinical or diagnostic observations only;
	intervention not indicated
2	Moderate; minimal, local or noninvasive intervention indicated; limiting age-
	appropriate instrumental activities of daily living (ADL)
3	Severe or medically significant but not immediately life-threatening hospitalization
	or prolongation of existing hospitalization indicated; disabling; limiting self care
	ADL
4	Life-threatening consequences; urgent intervention indicated
5	Death related to AE

Action taken

The investigator should record what action, if any, was taken to the planned administration of the investigational product due to the AE (i.e., discontinuation, modification, or interruption of the treatment).

Version #11, Date: 04-29-2015 Page 29 of 52

Relationship to the investigational product

When recording and reporting an AE or SAE, the investigator will provide an assessment of the relationship between the AE or SAE and the study drug(s) and/or study procedure. Related AEs or SAEs are those that are judged to be possibly or definitely related by the investigator. Unrelated AEs or SAEs are those that are judged to be unlikely or not related to the study drug(s) by the investigator. Definitions of relationship criteria are as follows:

Related

Definitely related: There is strong evidence that there is a causal relationship between exposure and AE

Possibly related: There is some evidence supporting the possibility of a causal relationship between exposure and AE

Unrelated

Remote/Unlikely related: There is no evidence of a causal relationship between exposure and AE; however, such a relationship cannot be ruled out

Unrelated: There is no suspicion of a causal relationship between exposure and AE

Describe all known or potential risks associated with this Investigational Drug/Device/Procedure. Include Adverse Event description, grade, expectedness, and attribution to the study treatment.

The most common adverse reactions ($\geq 10\%$) reported in patients who received Mozobil in conjunction with G-CSF regardless of causality and more frequent with Mozobil than placebo during hematopoietic stem cell mobilization and apheresis were diarrhea, nausea, fatigue, injections site reactions, headache, arthralgia, dizziness and vomiting. Per label (USPI) serious hypersensitivity reactions, including anaphylactic-type reactions, some of which have been life-threatening with clinically significant hypotension and shock, have occurred in patients receiving Plerixafor. In randomized studies, 34% of patients with non-Hodgkins's lymphoma and multiple myeloma had mild to moderate injection site reactions at the site of subcutaneous administration of Plerixafor. These included erythema, hematoma, hemorrhage, induration, inflammation, irritation, pain, paresthesia, pruritus, rash, swelling, and urticaria. Mild to moderate systemic reactions were observed in less than 1% of patients approximately 30 min after Plerixafor administration. Events included one or more of the following: urticaria (n = 2), periorbital swelling (n = 2), dyspnea (n = 1) or hypoxia (n = 1). Symptoms generally responded to treatments (e.g., antihistamines, corticosteroids, hydration or supplemental oxygen) or resolved spontaneously. Vasovagal reactions, orthostatic hypotension, and/or syncope can occur following subcutaneous injections. In Plerixafor oncology and healthy volunteer clinical studies, less than 1% of subjects experienced vasovagal reactions following subcutaneous administration of Plerixafor doses \leq 240 mg/kg. The majority of these events occurred within 1 hour of Plerixafor administration. Other adverse reactions that occurred in < 5% of patients but were reported as related to Plerixafor during mobilization and apheresis included abdominal pain,

Version #11, Date: 04-29-2015 Page 30 of 52

hyperhidrosis, abdominal distention, dry mouth, erythema, stomach discomfort, malaise, constipation, dyspepsia, and musculoskeletal pain.

In the study that assessed continuous infusion of Plerixafor over 10 days, four SAE's were noted: thrombocytopenia, infection of a PICC line and arrhythmia (> 25 PVC's/min) and panic attack associated with paresthesias [18].

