2.4 Study Design

For clinicaltrials.gov and Stanford Clinical Trials Directory compliance

- State the primary purpose for the protocol:
 - o Treatment
- State the interventional model from these choices:
 - Single Group
- State the number of intervention arms.
 - o One
- State whether the study will be masked (at least one party is unaware of the treatment)
 - o **Open**: no masking is used
- State whether the study is randomized.
 - o No
- State type of primary outcome or outcome that the protocol is designed to evaluate:

Safety (Phase I) Efficacy (Phase II)

Phase I

The Phase I is designed to evaluate safety. A total of 9 newly diagnosed patients will be enrolled within four weeks of surgery (biopsy, partial resection or gross total resection). In order to minimize the chances for local angiogenic migration into the irradiated field, irradiation will be administered to the area encompassed by T2 FLAIR imaging plus a 2 cm margin to 46 Gy with a focal boost to the enhancing area to 60 Gy over a six-week period. Temozolomide 75 mg/M²/d starting the day of radiotherapy will be administered for 42 days concurrent with irradiation. Eight days prior to irradiation completion, patients will have a PICC line placed. Seven days prior to irradiation completion, the continuous infusion of Plerixafor will be initiated using a step-wise dose escalation based on the modified toxicity probability interval (mTPI) method. All treatments will start one week prior to completion of radiotherapy with concurrent temozolomide for patients with newly diagnosed glioblastoma. This dose escalation study begins with an intermediate dose of 200 µg/kg per day for four weeks. The first 3 patients will be enrolled at this starting dose. Enrollment within a dose level will be staggered so that there is at least 1 week between patients. If tolerability and safety is established after the 4 week treatment period, then the fourth patient will be enrolled at the higher target dose of 400 µg/kg per day for four weeks. We will wait one week after the last infusion at one dose level before proceeding to the next dosage level.

If a patient experiences a DLT, then s/he will be removed from study and the next patient treated at the lower dose level as dictated by the mTPI table.

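### For a Plerixafor-related magnesium, calcium or potassium abnormality of grade 3 or worse, 7.1 lets the drug restart while 6.1, 4.2 and 2.4 treat the event as a DLT that ends treatment, and nothing says which prevails

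*Combined protocol and SAP*

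**What the plan says.** **Section 7.1 (Potential Adverse Events).** Because earlier studies saw premature ventricular contractions, "there will be a temporary interruption of plerixafor treatment for abnormalities in serum magnesium, calcium, or potassium at a Grade 2 or more severe". It continues: "The study medication may be resumed following correction of these electrolyte abnormalities as confirmed by repeat serum level testing". The same section lists "Clinically significant laboratory abnormalities" among the things that may be adverse events, and it classes events judged possibly related as related.

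**Section 6.1 (Dose Limiting Toxicities).** "DLT is defined as any hematologic or non-hematologic AE grade ≥3 with a suspected causal relationship to Plerixafor". The consequence is: "If a patient experiences a DLT, the infusion will be discontinued".

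**Section 4.2 (Criteria for Removal from Study).** The reasons for discontinuation or withdrawal include "DLT (any AEs with suspected causal relationship with Plerixafor >= grade 3", followed by cardiac examples.

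**Section 2.4 (Study Design), Phase I.** "If a patient experiences a DLT, then s/he will be removed from study", and the next patient is dosed according to the mTPI table.

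None of these sections refers to another on this point. Section 7.1 does not mention DLTs, and 6.1 and 4.2 make no exception for electrolytes. Nor does the DLT wording in 10.1.2.

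**The concern.** The electrolyte rule starts at grade 2 and runs upward without limit. The DLT rule starts at grade 3. Where they overlap, in related abnormalities of grade 3 or worse, one section permits a restart and another requires the infusion to end. An investigator with such a patient cannot both restart the drug and discontinue it.

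The occasions for this are regular. Section 4.0.1 and the study calendar call for chemistry that includes potassium, calcium and magnesium on Day 1, weekly during infusion, and also on Day 4 in Phase I. Arrhythmia is the hazard that the 7.1 paragraph was written to control.

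The statistical stake is the DLT count. DLT is the Phase I primary outcome (10.1.2), the only data that enter Table 12.1, and the trigger for the toxicity review in the expansion phase (12.1). If permission to resume were taken to mean that the event was not dose limiting, the count would be one too low.

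**Working it through.** **Step 1. Where the rules overlap.**

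| Mg, Ca or K abnormality | 7.1 | 6.1 / 4.2 / 2.4 | Conflict? |
|---|---|---|---|
| Grade 2, any cause | Interrupt; may resume | Not a DLT | No |
| Grade 3 or worse, not suspected related | Interrupt; may resume | Not a DLT | No |
| Grade 3 or worse, suspected related | Interrupt; may resume | DLT: discontinue / reason for discontinuation or withdrawal / remove from study | Yes |

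Only the last row conflicts.

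**Step 2. What the text says about the count.** The DLT definition in 6.1 covers any event of grade 3 or worse with suspected relation. Section 7.1 deals with giving the drug and exempts nothing from that definition. The literal count is therefore 1. A count of 0 needs an inference that the text does not make.

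**Step 3. Reproduce Table 12.1.** Inputs from 12.1: Beta(1,1) prior, target 0.30, precision ±0.05. With x DLTs in n patients the posterior is Beta(1+x, 1+n−x), with distribution function F. The mTPI rule compares posterior mass per unit length:

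- E: F(0.25)/0.25
- S: [F(0.35) − F(0.25)]/0.10
- D: [1 − F(0.35)]/0.65

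The largest value gives the action. It is replaced by U if P(p > 0.30) exceeds a cut-off. The documents do not give that cut-off, so 0.95 is assumed. With these settings all 54 printed cells are reproduced. With 0.90, five cells differ (D would become U). The cells used below are:

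| n, DLTs | F(0.25) | F(0.35) | E | S | D | Action (printed and computed) |
|---|---|---|---|---|---|---|
| 3, 0 | 0.6836 | 0.8215 | 2.734 | 1.379 | 0.275 | E |
| 3, 1 | 0.2617 | 0.4370 | 1.047 | 1.753 | 0.866 | S |
| 3, 2 | 0.0508 | 0.1265 | 0.203 | 0.757 | 1.344 | D |
| 6, 1 | 0.5551 | 0.7662 | 2.220 | 2.111 | 0.360 | E |
| 6, 2 | 0.2436 | 0.4677 | 0.974 | 2.241 | 0.819 | S |

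**Step 4. Effect of leaving out one DLT.**

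- n = 3, true count 1 recorded as 0: E instead of S.
- n = 3, true count 2 recorded as 1: S instead of D.
- n = 6, true count 2 recorded as 1: E instead of S.

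Across the table there are 1 + 2 + … + 9 = 45 pairs (n, x) and (n, x+1). The printed action differs in 21 of them. After applying the rule in 12.1 that at least 3 patients be studied at a dose before escalation, it differs in 20. In the other 45 − 20 = 25 pairs the action is the same either way. These are counts of table cells, not probabilities.

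**Step 5. Phase II.** The printed review limit is reached by one DLT in the first 5 patients. If the only DLT among those 5 is a related electrolyte event left uncounted, the recorded count is 0 and the review is not triggered.

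**The case against.** The strongest defence is that the sections can be read together. Section 7.1 treats electrolytes as an arrhythmia risk whatever the cause, and says only that the drug *may* be resumed. Section 6.1 covers related events of grade 3 or worse and says the infusion *will* be discontinued. On that reading one interrupts first, then applies the DLT rule if the event qualifies, and resumption is confined to grade 2 or unrelated events. The reading is sensible, but it is not written. It puts a ceiling on 7.1 that the words about greater severity do not contain. Section 6.2, on allergic reactions, does separate grades 1 and 2 from grade 3 and higher; 7.1 does not.

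A reader might go further and infer that the documents leave the count itself open, so that the same event scores 0 or 1. They do not: as shown above, the literal count is 1. This part of the defence stands, and the effect on dosing is conditional on a misreading.

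Three limits on size also stand. First, most pairs in Table 12.1 give the same action with or without the extra event. Second, 6.1 and 12.1 also carry sentences that choose the next dose by when a DLT occurred, so the table may not be the only route to the next dose; the comparison here uses the table alone. Third, the documents give no rate of related grade 3 or worse electrolyte events for this regimen. The 10% grade 3 hypercalcemia in section 2.5 comes from a myeloma study with bortezomib, where the disease may explain it, so no probability of a changed decision is offered. In Phase II, reaching the limit prompts a review and not an automatic stop.

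**Conclusion.** The point holds as a contradiction about treatment. For a suspected-related magnesium, calcium or potassium abnormality of grade 3 or worse, 7.1 permits a restart that 6.1 rules out and that 4.2 and 2.4 do not accommodate, and the plan sets no precedence. This conclusion needs no assumption about event rates.

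The consequence for the DLT count is a risk and not a stated feature of the plan. It arises only if an investigator takes permission to resume as a sign that the event was not dose limiting. If that happens, one missing DLT can change the table action (20 of 45 pairs after the minimum of 3) or let the first Phase II review pass untriggered. With only 9 Phase I patients, a single count can matter. The table check assumes a 0.95 cut-off for U, but the three examples in Step 4 hold with the table exactly as printed.

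**What to change.** Reconcile 2.4, 4.2, 6.1 and 7.1 so that all four state one rule for magnesium, calcium and potassium abnormalities of grade 3 or worse with suspected relation to Plerixafor. The rule should say:

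1. whether the event is a DLT;
2. whether the infusion may restart after correction;
3. that Table 12.1 and the Phase II toxicity review score the event in the same way.

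Which clinical rule to adopt is for the sponsor to decide. Section 6 separately allows no delays for an individual patient except in renal impairment, which conflicts with the 7.1 interruption at every grade it covers. Removing that ban would not settle the present point, but one amendment could deal with both.

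The cost is a sentence or so in each affected section, with no extra patients, visits or tests.
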